dLPFC	Dorsolateral Prefrontal Cortex
DSMB	Data and Safety Monitoring Board
EC	Ethics Committee
eCRF	Electronic Case Report Form
ECT	Electroconvulsive Therapy
EEG	Electroencephalogram
ES	Effect Size
FDA	Food and Drug Administration
FDAAA	Food and Drug Administration Amendments Act (of 2007)
fMRI	functional Magnetic Resonance Imaging
GCP	Good Clinical Practice
GLP	Good Laboratory Practice
GMP	Good Manufacturing Practices

[figure not shown]
GSK-3 β	Glycogen Synthase Kinase 3 Beta
HAMD-17	Hamilton Depression Rating Scale, 17-item version
HCTZ	Hydrochlorothiazide
HIPAA	Health Insurance Portability and Accountability Act
IC	Informed Consent
ICH	International Conference on Harmonisation
ICMJE	International Committee of Medical Journal Editors
IL-1 β	Interleukin 1 Beta
IL-6	Interleukin 6
IL-8	Interleukin 8
iNOS	Inducible Nitric Oxide Synthase
IRB	Institutional Review Board
LED	Light Emitting Diodes
MDD	Major Depressive Disorder
MDSG	Mood Disorders Support Group
MFG	Medial Frontal Gyrus
MGH	Massachusetts General Hospital
MGH DCRP	Massachusetts General Hospital Depression and Clinical Research Program
MPE	Maximum Permissible Exposure
mPFC	medial Prefrontal Cortex
MR	Magnetic Resonance
MRI	Magnetic Resonance Imaging
mW	Milliwatt
N	Number (typically refers to participants)
NAMI	National Alliance on Mental Illness
nm	Nanometer(s)
NF- κ B	Nuclear Factor κ B
NIH	National Institutes of Health
NIH IC	National Institutes of Health Institute/Center
NIMH	National Institute of Mental Health
NIR	Near-infrared Radiation
NKI	Nathan Kline Institute
NO	Nitric Oxide
NSMHA	North Suffolk Mental Health Association
NYU	New York University
NYUMC	New York University Medical Center

OPD	Outpatient Psychiatry Department
OPRD	Outpatient Research Department
PBM	Photobiomodulation
PET	Positron Emission Tomography
PFC	Prefrontal Cortex
PHI	Protected Health Information
PI	Principal Investigator
PW	Pulsed Wave
QC	Quality Control
RCT	Randomized Controlled Trial
RNA	Ribonucleic Acid
ROI	Region of Interest
ROS	Reactive Oxygen Species
RF	Report Form
rTMS	repetitive Transcranial Magnetic Stimulation
SAE	Serious Adverse Event/Serious Adverse Experience
SAP	Statistical and Analytical Plan
SC	Steering Committee
SCID	Structured Clinical Interview for DSM Disorders
SD	Standard Deviation
SFG	Superior Frontal Gyrus
SNRI	Serotonin-Norepinephrine Reuptake Inhibitor
SOP	Standard Operating Procedure
SPECT	Single Proton Emission Computerized Tomography
SSRI	Selective Serotonin Reuptake Inhibitor
TBI	Traumatic Brain Injury
tDCS	Transcranial Direct Current Stimulation
TNF- α	Tumor Necrosis Factor alpha
TSH	Thyroid Stimulating Hormone
t-PBM	transcranial Photobiomodulation
UP	Unanticipated Problem
VNS	Vagal Nerve Stimulation
VRP	Volunteer Recruitment Pool
WBC	White Blood Cells

Protocol Summary

Title	Transcranial Near Infrared Radiation and Cerebral Blood Flow in Depression
Short Title	TRIADE
Brief Summary	This study will compare the effect of three t-PBM doses (high, middle, and low irradiance) to sham t-PBM on PFC CBF as assessed with fMRI (BOLD) in this multi-center, phase I, single-blind, dose-ranging, controlled, crossover study of 30 subjects with MDD. All eligible participants will undergo four sessions of t-PBM during fMRI so that they experience irradiances of 50, 300 and ≥ 700 mW/cm ² as well as sham. The order of dose administration will be randomized and t-PBM will be administered with the LightForce® EXPi Deep Tissue Laser Therapy™ System, Transcranial PhotoBioModulation-1000 (tPBM-2.0).
Phase	I
Objectives	Primary : To identify the t-PBM irradiance dose (50, 300, or ≥ 700 mW/cm ²) with the largest impact on PFC CBF in MDD. Secondary : To compare the safety and tolerability of three t-PBM irradiance doses.
Methodology	Single-blind, dose-ranging, controlled, crossover study.
Endpoint	Primary : t-PBM effects on BOLD signal. Secondary : t-PBM effects on the frequency and severity of adverse events and side effects.
Study Duration	24 months
Participant Duration	6-12 weeks
Duration of IP administration	4 sessions
Population	30 men and women ages 18-65 with MDD
Study Sites	NYUSOM, NKI, MGH
Number of participants	30
Description of Study Agent/Procedure	Transcranial photobiomodulator, delivers laser-generated NIR to forehead.
Reference Therapy	Sham
Key Procedures	4 Sessions of t-PBM during MR scanning
Statistical Analysis	For each subject at each t-PBM dose we will model the BOLD signal at specified ROIs as a function of dose (considered a categorical variable with 4 levels) using mixed effects models, including random subject intercepts to account for the potentially correlated measures on the same subject.

Schematic of Study Design

1 Key Roles

Principal Investigator, NYSOM and NKI

[name], MSc,
Associate Professor of Psychiatry
NYUSOM
Director, Clinical Research Department, Nathan Kline Institute for Psychiatric Research
[name]
[name]
[contact]

Director, Clinical Research Division
NKI

2.1 Background Information and Relevant Literature

2.1.1 Problem: Unmet Need for Accessible, Scalable, and Effective Treatments for Depression

Twenty-one million Americans (~10%) suffered from a depressive episode over the past year¹. Major depressive disorder (MDD) is the third leading cause of global disability²; the global cost of mental illness is expected to more than double by 2030, with depressive disorders at the forefront³. Sadly, 43% of primary care patients experiencing a six-month depressive episode remain untreated, with most preferring self-management⁴ over professional help and/or prescription medications^{5,6}. Factors limiting the adoption of firstline interventions for MDD include burdensome side effects of medications^{7,8} and the time commitment for psychotherapies⁹. Somatic therapies such as electroconvulsive therapy (ECT), repetitive transcranial magnetic stimulation (rTMS) and vagus nerve stimulation (VNS) are approved for treatment resistant MDD¹⁰; however, they are unsuitable to become first line treatments, since they require in-office administration, and sometimes anesthesia and/or surgical procedures¹⁰. In contrast, the use of wellness devices is especially popular, since nearly 25% of Americans own a wearable device¹¹. **A new generation of at-home devices for MDD that are safe, well-tolerated, inexpensive and easy to use, would represent a valuable firstline intervention, both accessible and scalable.**

2.1.2 Potential Solution: Transcranial Photobiomodulation (t-PBM)

Transcranial photobiomodulation (t-PBM) is a novel neuromodulation based on non-retinal exposure to light at specific wavelengths. As summarized below, a substantial body of literature proves that transcranial photobiomodulation (t-PBM) with near-infrared (NIR) light penetrates deeply into the cerebral cortex¹²⁻¹⁴, modulates cortical excitability^{15,16} and improves cerebral perfusion¹⁷⁻¹⁹ and oxygenation²⁰. Its safety was demonstrated in 1,410 acute stroke patients^{21-23,102}. Antidepressant effects of t-PBM have been reported in both animal models²⁴⁻²⁸ and human studies²⁹⁻³⁴. In a double-blind clinical trial (n=21), our team demonstrated the antidepressant effect of adjunct t-PBM NIR delivered to the prefrontal cortex (PFC) over 8 weeks³⁵. Devices capable of administering t-PBM are already FDA- approved and can be manufactured with basic and relatively inexpensive lasers or light emitting diodes (LEDs). Due to its low cost, excellent safety profile, and ease of administration, PBM has the potential to become widely accessible. However, despite its clear advantages, no consensus exists on the optimal dose irradiance of t-PBM for MDD.

2.1.3 t-PBM Penetration: NIR undergoes exponential decay of the photon flux as it travels through tissues. Nevertheless, a small but significant fraction of the light delivered to the scalp reaches the cortex. Depending on parameters used, the distribution of the therapeutic dose (sufficient energy deposition for therapeutic effects) might vary from only the most superficial cortex to the whole cortical width, always in proximity of the light source⁵¹. While therapeutic NIR penetration varies based on wavelength^{13,14}, light source (LED versus laser)¹², pulsing⁵² and intensity^{12,13}, a 2% to 3% penetration rate of NIR is attainable at target prefrontal cortex regions. This corresponds to an NIR penetration of about 2 cm of intervening skin, skull, meninges, cerebrospinal fluid and brain. The magnitude of NIR fluence (energy density, J/cm²) to the skin surface –necessary to reach target areas of the brain therapeutically– is both safe and well tolerated. It is feasible to attain an NIR fluence on the human brain equivalent to the fluence inducing neurological benefits in animal models⁵³.

2.1.4 t-PBM Effects on Cerebral Blood Flow (CBF): In vivo t-PBM has robust and immediate effects on CBF. In rats, t-PBM at 660 nm with a LED device (9 mW/cm²) was associated with increased oxygen consumption in the frontal cortex⁹⁵, while in mice NIR (808 nm) t-PBM with laser (1.6 W/cm²) resulted in 30% increased CBF⁹⁶. In healthy humans, t-PBM with a 3.4W laser (1064 nm) led to increased

concentration of oxygenated hemoglobin²⁰, while in elderly women t-PBM with a 0.2W LED (627 nm) increased blood flow in the middle cerebral and basilar arteries¹⁹. In chronic traumatic brain injury (TBI) patients, t-PBM with a 3.3W LED device (629 and 850nm) increased CBF (measured by SPECT)³⁶. Our own preliminary data (Section 2.4) show immediate increase in CBF [measured as blood-oxygenation-level dependent (BOLD) signal on fMRI] in healthy volunteers exposed to 808 nm laser NIR. Therefore, changes in CBF during t-PBM administration, measured as changes in BOLD fMRI signal, is an excellent target engagement biomarker. Secondarily, t-PBM also has a modulatory effect on cortical excitability, reducing motor evoked potentials elicited by TMS¹⁵ and may result in increased functional connectivity in the default mode network⁹⁷.

2.1.5 t-PBM Cellular Mechanisms: The NIR delivered through t-PBM is absorbed by a mitochondrial enzyme and chromophore, cytochrome c oxidase (CCO), and is only minimally dissipated as thermal energy^{53,54}. The peak absorption of light energy by CCO occurs at four different wavelengths; one of these peaks is 812–846 nm⁵⁵, overlapping with the wavelengths with best brain penetration described above.

Depression is associated with hypometabolism in specific brain areas⁵⁶⁻⁵⁹ and mitochondrial dysfunction⁶⁰⁻⁶⁴. Results in cellular and animal models indicate that PBM can enhance mitochondrial activity. NIR delivers energy to the CCO and stimulates the mitochondrial respiratory chain leading to increased ATP production^{54,65,66}. In addition, NIR can improve mitochondrial activity by promoting the dissociation of nitric oxide (NO) from the CCO releasing the binding site for oxygen and restoring oxidative phosphorylation⁵³. The released NO may also act as a local vasodilator⁶⁷. A study on isolated mitochondria also reported increased RNA and protein synthesis after irradiation with a low-level laser (632.8 nm)⁶⁸.

Animal research suggests that PBM might also exert, via its impact on mitochondria, beneficial effects on several other pathophysiological mechanisms implicated in MDD, such as oxidative stress⁶⁹⁻⁷³, neuroinflammation⁷⁴⁻⁷⁸, and deficits in neuroplasticity and brain derived neurotrophic factor (BDNF)⁷⁹⁻⁸¹, and default mode network connectivity⁹⁷. NIR can induce short bursts of reactive oxygen species (ROS) leading to the activation of antioxidant mechanisms and the activation of the transcription factor nuclear factor κB (NF-κB), resulting in decreased overexpression of the inducible form of nitric oxide synthase (iNOS) and reduction of oxidative stress^{67,82,83}. In animal models, NIR light (600 to 1000 nm) reduced neuroinflammation by decreasing proinflammatory cytokines such as IL-6, TNF-α, IL-1β, and IL-8⁸⁴⁻⁸⁶, and decreasing the infiltration of macrophages, activated microglia and T lymphocytes to the CNS⁸⁶. In animal studies PBM also stimulates neurogenesis and neuroprotective mechanisms in models of neuronal injury, possibly mediated by increased BDNF and by inhibition of GSK-3β and pro-apoptotic molecules^{67,87-94}.

2.1.6 t-PBM Safety and Tolerability: The safety of one session of t-PBM was evaluated in three large RCTs with a pooled sample of 1,410 subjects with stroke^{21,22,100}. No significant difference in the rate of adverse effects were observed between the group receiving laser NIR (808 nm; 5W) or sham. No serious adverse events were found in our review of the literature³³. Two open studies using 1 and 6 sessions of t-PBM reported no treatment-emergent side-effects^{29,30}. A clinical trial with 16 t-PBM sessions reported an increased number of mild side-effects in the active treatment group, the most frequent being insomnia, “seeing vivid colors”, “an ashtray-like taste”, and irritable mood³⁵. Other potential risks relate to inappropriate administration and will be mitigated by the safety procedures. The risk of thermal injury from t-PBM delivered with the parameters used in the studies we reviewed is considered minimal and limited to the skin. In ten individuals treated for TBI with 10-15W lasers –a much higher power than what is used in t-PBM– the skin temperature increased to no more than 30°C with rapid cooling after removal of the NIR light. Clinically, patients reported slight skin warming, but no discomfort¹⁰¹. Laser devices have a potential risk of retinal lesions when used improperly; this is mitigated with appropriate safety eye gear and procedures.

2.1.7 t-PBM Effects on Depression: Multiple pre-clinical studies support the efficacy of t-PBM, in single or repeated administration, on animal models of depression such as the forced swim test^{24,27,90,98}, tail suspension test^{27,90}, mild chronic stress^{26,28}, or the reserpine-induced depression²⁴. In several of these studies the antidepressant effects were associated with biological effects related to mitochondrial stimulation, such as increased ATP biosynthesis and mitochondrial complex IV expression and activity in the prefrontal cortex (PFC)²⁷ and increased hippocampal neurogenesis⁹⁸. All clinical studies using t-PBM

for MDD reported in the literature aimed to modulate the forebrain, consistently with the dysfunction of the prefrontal cortex associated with MDD⁹⁹. In pilot studies with open designs, NIR was associated with an antidepressant response after a single²⁹ or repeated (6) administrations³⁰. Our recent RCT showed t-PBM was more efficacious than sham in 21 MDD subjects receiving bilateral t-PBM at 823 nm or sham directed on dorsolateral PFC (dIPFC, EEG sites F3 and F4) twice-a-week for 8 weeks³⁵. Another study suggested that t-PBM paired with a cognitive therapy may be effective in depression³⁴. All these studies measured acute, short term effects; only a case report describes persistence of effects over 9 months of repeated administration in a subject with MDD³².

2.1.8 Scales and Measures: The following clinician-administered scales and patient-reported measures will be utilized in the study.

- **(M.I.N.I)⁴⁰** – The M.I.N.I. is a short structured diagnostic interview, developed jointly by psychiatrists and clinicians in the United States and Europe, for DSM and ICD psychiatric disorders. With an administration time of approximately 15 minutes, it is designed to meet the need for a short but accurate structured psychiatric interview for clinical trials. According to researchers at the National Institute of Mental Health's (NIMH) Division of Clinical and Treatment Research, the M.I.N.I. is a fully validated and more time-efficient alternative to the Structured Clinical Interview for DSM Disorders (SCID).
- **Inventory of Depressive Symptomatology(IDS)⁴¹** – This is a 30-item clinician-rated inventory of depressive symptoms such as sleep, depressed mood, appetite, concentration, suicidal ideation, interest, energy, psychomotor retardation or agitation.
- **Montreal Cognitive Assessment (MoCA)⁴²** – This is a 10-item rapid screening instrument for mild cognitive dysfunction. It assesses different cognitive domains: attention and concentration, executive functions, memory, language, visuoconstructional skills, conceptual thinking, calculations, and orientation. This measure will be used to assess entry criteria.
- **The Massachusetts General Hospital (MGH) Antidepressant Treatment Response Questionnaire (ATRQ)⁴³** – This scale is used to determine treatment resistance in major depressive disorder (MDD). The ATRQ examines the efficacy (improvement from 0% [not improved at all] to 100% [completely improved]), and adequacy (adequate duration and dose) of any antidepressant treatment in a step-by-step procedure.
- **New Immigrant Survey-Skin Color Scale (NIS-SCS)⁴⁴** – The scale is an 11-point scale, ranging from zero to 10, with zero representing albinism, or the total absence of color, and 10 representing the darkest possible skin. The ten shades of skin color corresponding to the points 1 to 10 on the Massey and Martin Skin Color Scale are depicted in a chart, with each point represented by a hand, of identical form, but differing in color. The respondent never sees the chart. We gather this data for use as a potential covariate in analyses as skin color can affect absorption of NIR.
- **Systematic Assessment for Treatment Emergent Events (SAFTEE)⁴⁵** – The SAFTEE is a commonly used instrument originally developed by NIMH and adapted into a self-report instrument. The version of the scale that we plan to use is the same used by the multi-center, NIMH-sponsored CO-MED trial, and it examines in a systematic fashion all possible treatment-emergent side effects and probes specific adverse symptoms, including suicidal thoughts and behaviors, and self-injurious behavior.
- **Columbia Suicide Severity Rating Scale (C-SSRS)¹¹⁰** – An instrument endorsed by the FDA for clinical trials. This instrument systematically tracks suicidal ideation and behavior (e.g., suicide attempts, wish to die, thoughts of suicide, plan and intent).

- **Clinical Global Impressions – Severity and Improvement (CGI-S, CGI-I)** – These two instruments are scored 1-7 by the clinician based on assessment of the subject's overall clinical status. They measure, based on history and scores on other instruments: (a) depressive severity (CGI-S) and (b) clinical improvement (CGI-I).
- **The Potential Confounders Questionnaire (PCQ)** –This questionnaire solicits information about sleep, presence of jet lag, diet change, and the intake of over-the-counter drugs, prescription medications, caffeine, alcohol, nicotine, marijuana, and other street drugs.
- **The Perceptions of Blinding Questionnaire (PBQ) –The Perceptions of Blinding Questionnaire (PBQ)** – The PBQ is a self-report questionnaire to determine the degree to which the participant believes s/he is receiving the treatment or the sham.
- **Positive and Negative Affect Schedule (PANAS)⁴⁶** –This 20 item scale measures positive affect (e.g., excited, inspired) and negative affect (e.g., upset, afraid). Each item is rated on a five-point Likert Scale, ranging from 1 = *Very Slightly or Not at all*, to 5 = *Extremely*.
- **Montgomery-Åsberg Depression Rating Scale (MADRS)⁴⁷** –This 10-item clinician-rated instrument measures depression severity. It will be administered with a structured interview guide. The time frame for this scale is the past 7 days
- **Symptoms of Depression Questionnaire (SDQ)⁴⁸** – This is a comprehensive measure of depression that includes the assessment of symptoms in the anxiety–depression spectrum. It assesses irritability, anger attacks, and anxiety symptoms together with the commonly considered symptoms of depression. Analysis of the factor structure of the SDQ identified 5 subscales, including one in the anxiety–depression spectrum, with adequate internal consistency and concurrent validity.
- **Anxiety Symptoms Questionnaire (ASQ)⁴⁹** – This, is a 17-item self-report questionnaire measuring the frequency and intensity of 17 symptoms of anxiety, including nervousness, worrying, irritability, trouble relaxing, insomnia, lack of energy, difficulty concentrating, somatic symptoms, and impairment in functioning due to anxiety.
- **Adverse Events Form**- The Adverse Events Form captures any adverse event (serious or otherwise) specifically related to the application of the t-PBM.
- **Concomitant medications and therapies form** – This form records all ongoing medications, as well as other therapies targeting depression, and will be completed at every study visit, including the screening visit, as a safety-monitoring tool.
- **Quality of Life in Neurological Disorders, Cognitive Section (Neuro-QoL)⁵⁰** - The cognitive section of the Neuro-QoL is an 8 item self-rated measure of both executive function and general concerns. It measures perceived difficulties in cognitive abilities (e.g., memory, attention, and decision making) or in the application of such abilities to everyday tasks (e.g., planning, organizing, calculating, remembering, and learning).
- **Quality of Life, Enjoyment, and Satisfaction Questionnaire (Q-LES-Q)¹¹¹**- Assesses subjective quality of life (i.e. physical health, subjective feelings, leisure activities and social relationships).
- **MRI Safety Checklist**- Identifies risk factors that may make MRI participation unsafe.
- **The t-PBM Self-Report Questionnaire (TSRQ)** – An open-ended questionnaire focusing on potential inconveniences and discomforts from the t-PBM.

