3.5.2 Secondary Study Endpoints

The secondary endpoints will be t-PBM effects on brain temperature, suicidal ideation/behavior, and the frequency and severity of adverse events and side effects occurring at the time of each t-PBM session and between each t-PBM session and the subsequent study visit. Brain temperature will be assessed with MR; suicidal ideation/behavior with the C-SSRS. Adverse events will be tracked with the adverse events log; side effects, with the SAFTEE and TSRQ.

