6.2.3 Experimental Phase

Duration: 4 visits over 4-8 weeks

Timing: No more than 2 weeks between each visit.

While the provision of study treatment requires clinic attendance, we may conduct other components of the experimental visits remotely.

At each of the four visits, study staff will:

- *Record vital signs;
- Administer
MADRS,
CGI-I (except Visit 1 as this will be considered a baseline rating),
CGI-S,
C-SSRS, and
- MRI Safety Checklist; Record concomitant medications/therapies;
- *Administer the t-PBM session during MR Scanning;
- Record adverse events as reported by participant or observed by investigator.

In addition, participants will complete:

- PANAS,
- PBQ
- PCQ
- SDQ,
- ASQ,
- SAFTEE

- Neuro-QoL
- Q-LES-Q-SF, and
- TSRQ

MGH Site Neuronavigation: The BrainSight Neuronavigation System will be used at the MGH site to track the initial placement of the laser device on the subject's forehead and will be utilized to ensure accurate replication of positioning at each experimental visit. This is a recording device that does not involve any added risk or stimulation. Traditionally, this device is used to record precise location of EEG electrodes and transcranial magnetic stimulation (TMS) coils. In our case, we will be using it to record the position of the outlet of the laser before every PBM session. The BrainSight Neuronavigation System is FDA approved and is used as indicated. This device bounces light off of trackers that are placed on the forehead. Study staff lightly place a wand at various spots on the head. The system correlates the position of the wand with that of the trackers to precisely record the location of the head in relation to the photobiomodulation stimulation device. This is useful for later analysis, in which we will co-register the recorded laser position to the subject's MRI.

- For the NKI/NYU scans, lipid capsules are affixed to the device for demarcation of device location in the scans.

MR: Scanning will begin with acquisition of structural images and (for most subjects) a baseline MR thermometry scan. Subsequently we will collect approximately 60 minutes of functional data collection including ~20 minutes before t-PBM, ~20 minutes coinciding with t-PBM, and ~20 minutes following t-PBM, as well as (for most subjects) a post-t-PBM MR thermometry scan. (For technical and logistical reasons, we may opt to skip the thermometry scan for some subjects.)

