7.1.1 Definition of Adverse Events (AE)

An **adverse event** (AE) is any symptom, sign, illness or experience that develops or worsens in severity during the course of the study. Intercurrent illnesses or injuries should be regarded as adverse events. Abnormal results of diagnostic procedures are considered to be adverse events if the abnormality:

- results in study withdrawal;
- is associated with a serious adverse event;
- is associated with clinical signs or symptoms;
- leads to additional treatment or to further diagnostic tests; and/or
- is considered by the investigator to be of clinical significance.

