7.2.2 Relationship to Study Agent

The clinician's assessment of an AE's relationship to study device is part of the documentation process, but it is not a factor in determining what is or is not reported in the study. If there is any doubt as to whether a clinical observation is an AE, the event should be reported. All AEs must have their relationship to study agent assessed. To help assess, the following guidelines are used.

For all collected AEs, the clinician who examines and evaluates the participant will determine the AE's causality based on temporal relationship and his/her clinical judgment. Evaluation of relatedness must consider etiologies such as natural history of the underlying disease, concurrent illness, concomitant therapy, study-related procedures, accidents, and other external factors. The degree of certainty about causality will be graded using the categories below.

- **Definitely Related** – There is clear evidence to suggest a causal relationship, and other possible contributing factors can be ruled out. The clinical event, including an abnormal laboratory test result, occurs in a plausible time relationship to drug administration and cannot be explained by concurrent disease or other drugs or chemicals. The response to withdrawal of the drug (dechallenge) should be clinically plausible. The event must be pharmacologically or phenomenologically definitive, with use of a satisfactory rechallenge procedure if necessary.
- **Probably Related** – There is evidence to suggest a causal relationship, and the influence of other factors is unlikely. The clinical event, including an abnormal laboratory test result, occurs within a reasonable time after administration of the drug, is unlikely to be attributed to concurrent disease or other drugs or chemicals, and follows a clinically reasonable response on withdrawal (dechallenge). Rechallenge information is not required to fulfill this definition.
- **Possibly Related** – There is some evidence to suggest a causal relationship (e.g., the event occurred within a reasonable time after administration of the trial medication). However, other factors may have contributed to the event (e.g., the participant's clinical condition, other concomitant events). Although an AE may rate only as "possibly related" soon after discovery, it can be flagged as requiring more information and later be upgraded to "probably related" or "definitely related," as appropriate.

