7.3 Time Period and Frequency for Event Assessment and Follow-Up

The occurrence of an AE or SAE may come to the attention of study personnel during study visits and interviews of a study participant presenting for medical care, or upon review by a study monitor. All AEs including local and systemic reactions not meeting the criteria for SAEs will be captured on the appropriate RF. Information to be collected includes event description, time of onset, clinician's assessment of severity, relationship to study product (assessed only by those with the training and authority to make a diagnosis), and time of resolution/stabilization of the event. All AEs occurring while on

study must be documented appropriately regardless of relationship. All AEs will be followed to adequate resolution.

Any medical condition that is present at the time that the participant is screened will be considered as baseline and not reported as an AE. However, if the study participant's condition deteriorates at any time during the study, it will be recorded as an AE. UPs will be recorded in the data collection system throughout the study.

Changes in the severity of an AE will be documented to allow an assessment of the duration of the event at each level of severity to be performed. AEs characterized as intermittent require documentation of onset and duration of each episode.

The PI will record all reportable events with start dates occurring any time after informed consent is obtained until 7 (for non-serious AEs) or 30 days (for SAEs) after the last day of study participation. At each study visit, the investigator will inquire about the occurrence of AE/SAEs since the last visit. Events will be followed for outcome information until resolution or stabilization.

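### Section 2.1.8 limits the Adverse Events Form to events related to t-PBM, while 7.1.1, 7.2.2 and 7.3 require every adverse event to be recorded, so the AE-log part of the secondary endpoint could rest on a filtered count

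*Combined protocol and SAP*

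**What the plan says.** Two descriptions of adverse event recording stand side by side.

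**The instrument.** Section 2.1.8 lists the study's scales and forms. It says that the Adverse Events Form "captures any adverse event (serious or otherwise) specifically related to the application of the t-PBM".

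**The safety sections.** None of these makes recording depend on relatedness:
- Section 7.1.1 defines an adverse event as "any symptom, sign, illness or experience that develops or worsens in severity during the course of the study".
- Section 7.2.2 says of the relationship assessment that "it is not a factor in determining what is or is not reported in the study". It adds: "All AEs must have their relationship to study agent assessed". The scale runs from definitely related to not related.
- Section 7.3 says that events on "study must be documented appropriately regardless of relationship", and sets the recording window from informed consent. Non-serious events "will be captured on the appropriate RF", and that form is not named.
- Section 6.2.3 gives the visit procedure: "Record adverse events as reported by participant or observed by investigator".

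**Use of the data.** Section 3.5.2 places adverse events in the secondary endpoint: "Adverse events will be tracked with the adverse events log". Section 9.3.3 models the logs, SAFTEE and TSRQ by dose at four levels and estimates each active dose minus sham. Section 7.8 has the DSMB review events from the logs and receive unblinded rates by treatment group. The Schedule of Events lists an AE Form at the experimental visits and at follow-up, but not at screening, and lists no separate log.

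**The concern.** A form designed for related events only has no place for an event graded unlikely or not related, although section 7.2.2 requires those grades. If the form is what staff complete at a visit, its scope decides which events can later be counted.

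Adverse event frequency and severity by dose is one component of the secondary endpoint. The usual protection for such a comparison is to count every event in each condition and let the control absorb the background. If an investigator's causal judgement comes before recording, the comparison depends partly on that judgement. An effect that nobody yet attributes to the light could go unrecorded on this form. The DSMB's rates would carry the same filter, and section 7.8 sets no predetermined stopping rules, so the board relies on its reading of the data. Events never written down may not be recoverable at analysis.

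**Working it through.** The plan states no figure for this point, so the check is mainly a comparison of text. A short illustration of direction follows.

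**1. Do the sections conflict?** Take an event during the study that the clinician grades as not related. Under 7.1.1 it is an adverse event. Under 7.2.2 it is graded and its grade does not decide reporting. Under 7.3 it is documented. Under the definition in 2.1.8 it falls outside the form. The phrase in 2.1.8 covers serious events too, whereas sections 7.5 and 7.8 require serious events to be reported whatever their relationship. The conflict is real.

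**2. Does the form feed the endpoint?** Sections 3.5.2, 7.8 and 9.3.3 name the log or logs, and 2.1.8 and the Schedule of Events name the form. No section equates them, and none describes a second record that holds unrelated events. That the form is the source of the log is therefore an inference.

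**3. Does the timing match?** Section 7.3 starts recording at consent. The schedule does not mark the AE Form at screening. Events before the first session do not enter the by-dose comparison, so this second mismatch concerns completeness of safety recording.

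**4. What would a filter do?** The event rates and the shares judged related below are assumptions. Only the 24 observations per dose come from the plan (section 9.4: 30 participants less 20% dropout, 30 × 0.8 = 24).

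Expected count on the form = 24 × p × k, where p is the true event rate and k the share judged related. Apparent difference = p(active) × k(active) − p(sham) × k(sham).

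| True rate, sham / active | Share judged related, sham / active | Count, sham / active | Apparent difference |
|---|---|---|---|
| 30% / 30% | 100% / 100% | 7.2 / 7.2 | 0 points |
| 30% / 30% | 25% / 25% | 1.8 / 1.8 | 0 points |
| 30% / 30% | 25% / 50% | 1.8 / 3.6 | 7.5 points |
| 30% / 30% | 25% / 75% | 1.8 / 5.4 | 15 points |
| 30% / 50% | 100% / 100% | 7.2 / 12.0 | 20 points |
| 30% / 50% | 50% / 50% | 3.6 / 6.0 | 10 points |
| 30% / 50% | 25% / 25% | 1.8 / 3.0 | 5 points |

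A filter applied equally to all sessions creates no difference where none exists, but shrinks a true one in proportion to k. The ratio of expected counts is unchanged (12.0 / 7.2 = 3.0 / 1.8 = 1.67), but it rests on far fewer events. A filter applied unequally can produce a difference from nothing.

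**The case against.** The strongest reply is that the sentence in 2.1.8 is a one-line description in a background section, and that every operative safety section goes the other way. Sections 6.2.3, 7.1.1, 7.2.2 and 7.3 all call for unfiltered recording, and a site that follows section 7 will not filter. Loose drafting is a fair reading. This stands, and it limits what can be said about the consequence. It does not settle which text the form follows: the form is not in the documents, and the neighbouring entry in 2.1.8 gives the concomitant medications form an explicitly unrestricted scope.

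Three stronger readings are tempting, and the documents do not support them.

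- *A reader might infer that sham counts fall by construction.* Section 5.1.3 lists sham t-PBM among the sessions, and section 9.5.1 describes a heating element that activates during sham. An event after sham can be judged related to the application.
- *A reader might infer that every dose-sham difference is biased.* With equal true rates and the same judgement in every session, the expected difference stays at zero. A false difference needs relatedness to be judged differently by dose. Whether staff could do so is unclear: the Protocol Summary and section 3.4 call the study single-blind, while section 5.1.3 says that participant and staff are both blind.
- *A reader might infer that unexpected effects are lost altogether.* SAFTEE is a systematic self-report of treatment-emergent effects, completed at each experimental visit and at follow-up and modelled by dose. It has no investigator filter. C-SSRS and brain temperature are also separate. TSRQ is separate too, but covers only inconveniences and discomforts from t-PBM. Since section 3.5.2 assigns adverse events to the log and side effects to SAFTEE and TSRQ, these measures reduce the gap without closing it.

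**Conclusion.** The contradiction between section 2.1.8 and sections 7.1.1, 7.2.2 and 7.3 is established from the text and should be corrected. It is more than editorial, because a form restricted to related events cannot hold the lower relatedness grades that the protocol requires.

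The consequence is conditional on two things: that sites work to the wording in 2.1.8 and not to section 7, and that the form is the source of the adverse events log. If both hold, the AE-log part of the secondary endpoint and the DSMB's rates by group rest on a filtered count. On the difference scale this shrinks true effects. It creates false ones only if relatedness is also judged differently by dose. The size cannot be derived from the documents, and the table above shows direction under assumed values only. The other secondary measures are not affected through this route.

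**What to change.** Four edits, none of which alters the design:

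1. In 2.1.8, define the Adverse Events Form as recording all adverse events from consent onward, with relatedness as a field on the form. Check that the form in use matches.
2. In the Schedule of Events, mark the AE Form at screening, to agree with section 7.3.
3. State that the Adverse Events Form and the adverse events log are the same record.
4. In 9.3.3, state that the by-dose comparison uses all adverse events, with related events shown as a subset.

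The cost is a few sentences, one schedule entry and a check of the form. Sections 7.2.2 and 7.3 already require the fuller recording, so the edits add no new collection duty. If enrolment has begun, entries already made should be checked against source notes for events left off as unrelated.
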